2.2. Study Populations

Safety population: All patients who receive at least one dose of the study drug will be included in the safety population

Efficacy population: Intent-to-treat (ITT) population with last observation carried forward (LOCF) in patients who receive at least one treatment with study drug and in whom CGM data was collected at least once during treatment.

2.3. Patient Disposition and Characteristics

An account of the patients by disposition will be tabulated overall. The number of patients included in each analysis population will be summarized. Patients not completing the study will be summarized and listed with the reason for their premature discontinuation. There will be an analysis of withdrawal rates by treatment group using both descriptive statistics and Fisher's exact test (2-sided and $\alpha=0.05$). A list of screening failures will also be provided.

2.4. Demographics and Patient Baseline Characteristics

Patient demography will be presented using summary statistics (N, mean, standard deviation, median, minimum and maximum) for continuous measurements, or frequency tables (numbers and percentages) for categorical measurements.

2.5. Study Drug Duration and Compliance

During the run-in period four doses of placebo (8 capsules) will be dispensed to subjects for Day 1 and Day 2. Compliance will be reviewed during admission on Day 2 to protect the single-blind nature of this treatment.

All doses of study treatment will be administered in the CRU. Oral dosing compliance will be ascertained by inspection of the oral cavity (mouth check) following dosing.

This study does not include dose modifications.

2.6. Prior and Concomitant Medications

Prior and concomitant medications will be coded using World Health Organization (WHO) Drug dictionary March 1, 2013 version.

Prior medications will be defined as any medication that stops prior to the day of first dose.

Concomitant medications will be defined as any medication that stops on or after the day of first dose.

Section 2.13 describes the imputation rules for partial dates. All medications will be presented in a data listing.

2.7. Safety Evaluations

2.7.1. Adverse Events

Adverse events will be coded using the Medical Dictionary for Drug Regulatory Affairs (MedDRA) version 16.0 and tabulated, including categorical information of interest such as onset and resolution times, time of onset relative to dose, severity at onset, maximum severity, causal relationship to study medication, and action taken. The severity of AEs will be graded according to NCI CTCAE version 4.03.

Treatment-emergent adverse events (TEAEs) are defined as any AE that starts or increases in severity after the first randomized dose of study treatment on visit 2/Day 4. The incidence of TEAEs will be tabulated by MedDRA preferred term, system organ class, treatment group, severity, and assigned relationship to study treatment. Adverse events will also be summarized by severity and relationship to the investigational product (IP).

The incidence of serious AEs, drug-related AEs, serious and drug-related AEs, and any AEs resulting in discontinuation from the study will be listed.

2.7.2. Hypoglycemic Events

The proportion (percentage) of patients affected by hypoglycemia and event rates for each of the classifications of hypoglycemic events will be reported by treatment received. The time-distribution of hypoglycemic episodes per patient will be reported for each treatment group.

2.7.3. Safety Laboratory Evaluations

Screening and end of study results, together with changes from screening at end of study, will be described using summary statistics for each parameter. Changes from screening will be compared between treatments using an Analysis of Variance (ANOVA) model.

A clinically significant abnormal value or clinically significant change from baseline (Screening), may be recorded as an AE, if deemed appropriate by the PI or sponsor.

2.7.4. Vital Signs

Results, together with changes from baseline, will be described using summary statistics for each parameter for each day in which vital signs are collected. Changes from baseline will be compared between treatments using an ANOVA model.

A clinically significant change from baseline may be recorded as an AE, if deemed appropriate by the PI or sponsor.

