
Summary of Assessments
	
Safety will be verified by monitoring adverse events, clinical laboratory values, vital signs, physical examinations, and ECG.
 
CGM Monitoring will be used throughout the entire treatment period to compare pre-treatment, treatment, and post-treatment glucose levels, as well as post-prandial glucose.
 
Pharmacokinetics/Pharmacodynamics will be used to compare pre-treatment and post-treatment C-peptide and insulin levels.

Duration of Participation
	
Subjects will be evaluated for participation in the study during a 7-10 day Screening period. The planned length of participation is about 65 days (from Visit 2 through Visit 3). During each Visit 2 treatment Period, the subjects will be confined to the unit for 8 nights from check-in on the evening of Day 2 through completion of the post-treatment procedures on the morning of Day 10.

Subject Selection Criteria
	
This study will enroll T2DM subjects with an HbA_{1c} $\geq 7.5\%$ and $\leq 10.5\%$, who are taking metformin only, metformin in addition to sulfonylurea, metformin in addition to TZD, metformin in addition to an SGLT-2 inhibitor, or metformin in addition to a DPP-4 inhibitor with all treatment regimens stable for a minimum of 8 weeks prior to Visit 2/Period 1/Day 1.

Statistical Methods
	
Pharmacokinetics/Pharmacodynamics (PK/PD) The PK/PD analysis will be conducted using model-independent methods and will be based on plasma concentrations of insulin and C-peptide.
 
Continuous Glucose Monitoring The placebo adjusted change in means will be analyzed using an Analysis of Variance (ANOVA) with treatment as the main effect to

	
determine whether multiple doses a day has an effect on the CGM parameters.
 
The ratios of the placebo adjusted change in means between the active treatments within each subject will also be derived to estimate the magnitude of the dose response.
 
Summary statistics will be presented for both the placebo adjusted change in means and the ratios of the placebo adjusted change in means. Analysis results will be presented for the change in means.
 
Safety All safety parameters will be summarized and listed using descriptive statistics.

--	--

Table of Contents

TITLE PAGE	1
SPONSOR PROTOCOL APPROVAL SIGNATURE PAGE	2
INVESTIGATOR SIGNATURE PAGE	3
SYNOPSIS.....	4
LIST OF ABBREVIATIONS AND DEFINITIONS OF TERMS.....	11
1 INTRODUCTION	13
2 STUDY OBJECTIVES.....	15

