2 STUDY OBJECTIVES

2.1 Primary Objectives

- To compare pre-treatment (Day 3) to end of treatment (Day 8) 24-hour CGM glucose for single and multiple doses of ORMD-0801 vs placebo.
- To evaluate safety parameters for single and multiple doses of ORMD-0801 vs placebo.

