8.1 Sample Size

A total of 30 subjects will be randomized to receive either placebo, ORMD-0801 460 IU qd, ORMD-0801 460 IU bid, or ORMD-0801 460 IU tid during each treatment period.

Safety will be a secondary endpoint for this trial and will be assessed primarily based on AEs. Secondary safety assessments will include physical examination, 12-lead ECG, vital signs (including weight, seated SBP/DBP, heart rate, and temperature), and clinical safety labs (hematology, serum chemistry, and urinalysis).

This study is not powered for statistical significance.

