8.4.4 Vital Signs

Individual vital sign measurements (height, weight, seated SBP/DBP, heart rate, and temperature) will be listed by measurement time and summarized using descriptive statistics as appropriate (i.e., mean, median, range, and standard deviation). Individual change from baseline (predose Day 1) in vital sign measurements will be calculated and summarized descriptively. A clinically significant change from baseline (predose Day 1) will be recorded as a TEAE if deemed appropriate by the Investigator.

8.4.5 12-lead ECG

Individual 12-lead ECG assessments will be listed by visit and summarized using descriptive statistics as appropriate (i.e., mean, median, range, and standard deviation for continuous data and frequency for categorical data).

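### SAP 2.7.3 and 2.7.4 add between-treatment ANOVAs on laboratory and vital-sign changes where the protocol plans descriptive summaries only; no model, alpha or interpretation is given, and the laboratory comparison cannot be tied to a treatment

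*SAP*

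**What the plan says.** **Protocol.** The synopsis, under Statistical Methods, states: "All safety parameters will be summarized and listed using descriptive statistics". Section 8.4.3 plans descriptive summaries of laboratory changes. Section 8.4.4 does the same for vital signs and fixes the baseline: "Individual change from baseline (predose Day 1) in vital sign measurements will be calculated and summarized descriptively". Section 8.4.2 rules out inferential comparison of adverse events.

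**SAP.** Section 2.7.3 first plans summaries ("Screening and end of study results, together with changes from screening at end of study, will be described using summary statistics for each parameter") and then adds: "Changes from screening will be compared between treatments using an Analysis of Variance (ANOVA) model". In section 2.7.4, vital-sign results and changes from baseline "will be described using summary statistics for each parameter for each day in which vital signs are collected", after which: "Changes from baseline will be compared between treatments using an ANOVA model". Neither section gives model terms, an alpha, a key parameter or day, or a rule for reading the result. The SAP does not flag the departure from the protocol or define the vital-sign baseline.

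**Role of safety.** Protocol 2.1 lists as a primary objective: "To evaluate safety parameters for single and multiple doses of ORMD-0801 vs placebo". SAP 1.3.1 agrees. Protocol 8.1 says: "Safety will be a secondary endpoint for this trial and will be assessed primarily based on AEs".

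**The concern.** A hypothesis test is not a further detail of a descriptive plan; it is a different analysis. Once the tables carry p-values, someone has to read them, and the plan does not say how. Because safety is labelled both primary and secondary, a reader cannot tell whether these p-values bear on a primary objective.

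Both outcomes are open to misreading. Isolated small p-values can arise by chance across many measures and days. Large ones show little in a trial that both documents say was not sized for statistical power. There is also a question that comes before multiplicity: whether a change from screening to end of study can be compared between treatments at all when each subject receives three of them.

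**Working it through.** The documents give no alpha, power or error rate for these tests, so there is no plan figure to reproduce.

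**Laboratory ANOVA: which treatment does the change belong to?**

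1. SAP 2.7.3 uses one change per parameter, from screening to end of study.
2. Under Protocol 3.4 and 3.6, Visit 3 is 7 to 9 days after Day 10 of Period 3. The last double-blind dose is on Day 8, so the sample falls (10 - 8) + 7 = 9 to (10 - 8) + 9 = 11 days after it, and after all three treatments.
3. Haematology and urinalysis are taken only at Screening and at Visit 3 or early withdrawal. Chemistry is also taken on Days 3 and 8 of each period, but SAP 2.7.3 does not name those samples.
4. There are three ways to run the comparison, and the SAP chooses none:
   - Enter the single Visit 3 change under all three of a subject's treatments. The values are then identical across treatments within subject and cannot show a treatment effect. In simulation with 28 independent parameters (9 haematology, 19 chemistry; Protocol 6.3.5.1), the chance of any p<0.05 is about 0.001 to 0.002.
   - Assign it to the last treatment received. This is a between-subject comparison on 30 values, confounded with the two earlier treatments.
   - Assign it to no treatment. The test cannot then be run.

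**Vital-sign ANOVA: how many tests, and what error rate?**

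Inputs:
- Four measures have a change from Day 1: weight, systolic pressure, diastolic pressure and heart rate. Temperature is taken only on Day 2 (Protocol 6.3.2).
- Vital signs on Days 3-9 precede the morning dose, and the first randomised dose is on Day 4. The days after that dose are therefore Days 5-10, six days.
- 30 subjects each receive placebo plus two of three active regimens (Protocol 5.2). If balanced, this gives 30 placebo periods and 20 per active regimen, 90 in all.
- Alpha 0.05 is an assumption. The SAP states that level only for withdrawal rates (2.3).

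Tests if split by day: 4 x 6 = 24. Tests if not split: 4. For k independent tests, P(at least one false positive) = 1 - 0.95^k:
- k = 24: 1 - 0.95^24 = 0.71, with 24 x 0.05 = 1.2 expected false positives.
- k = 4: 1 - 0.95^4 = 0.19, with 4 x 0.05 = 0.2 expected.

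Days within a period are correlated, and so are periods within a subject, so these were simulated with no treatment effect (3,000 to 4,000 runs per setting; day-to-day correlation 0.3 to 0.8; the four measures independent; simulation error about 0.01). The one-way ANOVA has 90 - 4 = 86 error df. The model with subject, period and treatment has 90 - 1 - 29 - 2 - 3 = 55. The unsplit case tests the mean of Days 5-10.

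| Correlation between a subject's periods | 0 | 0.3 | 0.5 |
|---|---|---|---|
| 24 tests, one-way | 0.47-0.67 | 0.25-0.40 | 0.14-0.21 |
| 24 tests, subject and period in model | 0.47-0.69 | 0.47-0.69 | 0.47-0.69 |
| 4 tests, one-way | 0.18-0.20 | 0.08-0.09 | about 0.04 |
| 4 tests, subject and period in model | 0.18-0.20 | 0.18-0.20 | 0.18-0.20 |

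The one-way values fall because a test that ignores subject becomes conservative: the size of a single test drops from 0.05 to about 0.02 at correlation 0.3 and about 0.01 at 0.5. So the unstated model leaves either a mis-sized test or, if testing is daily, roughly an even or higher chance of a spurious result. The one-way reading is plausible, since SAP 2.8.2 uses a one-way ANOVA for the insulin and C-peptide areas.

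**The case against.** The strongest reply is that these tests decide nothing. No success, stopping or dosing rule uses them. Protocol 8.1 rests safety mainly on adverse events and treats vital signs and laboratory values as supportive. Protocol section 8 leaves further detail to the SAP, and safety screens are commonly left unadjusted. All of that stands, and it limits the weight of the point. It does not remove the conflict between a descriptive protocol and an inferential SAP, or make the laboratory comparison interpretable.

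A reader might go further in three ways that the documents do not support:
- *That chance differences will be reported as treatment effects.* Neither document says so. What can be said is that the SAP has no rule for reading them.
- *That every vital sign is tested on every day.* The wording about each day belongs to the sentence on summary statistics; the ANOVA sentence does not repeat it. Temperature cannot be included at all.
- *That the 28 haematology and chemistry parameters form a family of size-0.05 tests with a large chance of a false positive.* That assumes each change can be assigned to a treatment, which the sampling schedule does not allow for the analysis in SAP 2.7.3.

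**Conclusion.** The point holds as a conflict between the documents and as an analysis that is not specified well enough to run. The two textual findings, unplanned ANOVAs and the primary/secondary contradiction, need no simulation. The laboratory finding follows from the visit schedule: for completers, a screening-to-Visit 3 change cannot be assigned to one treatment.

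The vital-sign error rate is not a single number. It runs from about 0.04 to about 0.69, depending on whether testing is daily and whether subject is in the model. It rests on an assumed alpha of 0.05, balanced allocation, independent measures, and the stated ranges of correlation between days and periods. A false positive is therefore likely under some readings and unlikely under others, and the SAP does not say which applies. The 24-hour CGM analysis is not affected.

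**What to change.** - **SAP 2.7.3 and 2.7.4:** delete the ANOVA sentences and summarise descriptively, as the protocol specifies.
- **Vital signs:** summarise changes by treatment from predose Day 1 of the same period, and state that baseline in the SAP.
- **Laboratory:** summarise in-period chemistry by treatment (Day 3 to Day 8), and screening-to-Visit 3 changes overall, not by treatment.
- **If a between-treatment estimate is kept:** label it exploratory, use a model with subject, period and treatment, name the days, and make no significance claim. Replacing the p-values with unadjusted 95% confidence intervals against placebo would not be enough: each interval excludes zero by chance as often as its p-value falls below 0.05, and the protocol does not specify such intervals.
- **Protocol 8.1:** align with 2.1 by stating that the safety objective is assessed descriptively, primarily on adverse events.

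The cost is a few sentences in the SAP and one in the protocol, with no new data. The downside is that the report will carry no safety p-values.

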2.7.5. Electrocardiogram

Individual 12-lead ECG assessments will be listed by visit.

2.7.6. Physical Examination

The Screening and end of treatment results will be described using frequency counts for each body system.

2.7.7. Continuous Glucose Monitoring

The number of subjects who had at least one value < 60 , had at least one value ≥ 125 , had at least one value ≥ 150 , had at least one value ≥ 175 , had at least one value ≥ 200 , had at least one value ≥ 225 and had at least one value ≥ 250 will be summarized for the run-in and end of treatment periods for the following time intervals:

- 24 hour
- Daytime
- Nighttime

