4.3 Subject and Trial Discontinuation

Subjects may choose to withdraw from this study at any time for any reason without penalty of jeopardizing their health care or loss of benefits to which the subject is otherwise entitled.

Within the provisions of informed consent and good clinical judgment with respect to safety, every attempt will be made to have subjects complete the study. The following are reasons to terminate a subject's participation in the study:

1. Subject experiences an AE that in the judgement of the Investigator poses a significant risk to the subject for continued participation in the study.
2. Subject uses a prohibited medication (listed in Section 5.7) that in the judgment of the Investigator poses a significant risk to the subject for continued participation in the study or that will interfere with the interpretation of the results of the study.
3. Subject becomes pregnant.
4. Significant protocol violation or noncompliance on the part of the subject or the Investigator.
5. Intercurrent illness that requires treatment that is not consistent with the protocol requirements, or intercurrent illness or the associated treatment that in the judgment of the Investigator poses a significant risk to the subject for continued participation in the study.
6. Subject wishes to withdraw for any reason.
7. Sponsor elects to end the study, or the Investigational Site elects to end the study at their site.
8. Any other reason that in the judgment of the Investigator poses unacceptable risk to the subject.

Reasons for study drug discontinuation may include the following:

1. Pregnancy
2. Adverse event
3. Episodes of hypoglycemia as defined in Section 7.3.1.
4. Patient meets one of the exclusion criteria during the study
5. Any clinically significant change in the patient's medical condition

The occurrence of severe hypoglycemia (as defined in Section 7.3.1) in two patients during the double-blind treatment period will lead to unblinding of the treatment in those two patients.

Patients who withdraw from the study prior to treatment may be replaced. Patients who are withdrawn and have received at least one treatment will not be replaced. Patients who discontinue study drug treatment will not be replaced.

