1.3. Study Objectives

1.3.1 Primary Objectives

The primary objectives of this study are to compare pre-treatment (Day 3) to end of treatment (Day 8) 24-hour CGM glucose for single and multiple doses of ORMD-0801 vs placebo and to evaluate safety parameters for single and multiple dose of ORMD-0801 vs placebo.

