2.8. Efficacy Evaluations

2.8.1. Continuous Glucose Monitoring

The last 2 days with at least 80% of expected measurements prior to dosing will be considered the run-in days for each of the parameters. The last 2 days with at least 80% of expected measurements prior to 8 hours after the last dose will be considered the on treatment days. The measurements more than 8 hours after the last dose will be considered the follow-up days.

The 24-hr period (6AM to 6AM), nighttime (from 10pm to 6am), daytime (6AM to 10PM), and post-prandial (first hour after meal start time including breakfast, lunch, and dinner) glucose values will be summarized. The mean, standard deviation, minimum, maximum, first quartile, median, third quartile and inner-quartile range will be presented.

The area under the curve (AUC) will be derived for each of the time periods (24-hour, daytime and nighttime) using the indicated days (run-in days, treatment days and follow-up days). The average glucose measurement will be derived by dividing the AUC by the number of observed hours. The average change from run-in will be derived for each treatment regimen for both the treatment days and the follow-up days.

The placebo adjusted change in means will be derived for each of the active therapy regimens by subtracting the placebo mean (the mean change from run-in while the subject was receiving placebo) from the active therapy mean (the mean change from run-in while the subject was receiving the active therapy).

The placebo adjusted change in means will be derived for both the treatment days and the follow-up days. The placebo adjusted change in means will be analyzed using an Analysis of Variance (ANOVA) with treatment as the main effect to determine whether multiple doses a day has an effect on the CGM parameters. If the residuals are not normally distributed, then a Kruskal-Wallis test (one-way analysis of variance on the ranks) will be performed.

The ratios of the placebo adjusted change in means between the active treatments within each subject will also be derived to estimate the magnitude of the dose response.

Summary statistics will be presented for both the placebo adjusted change in means and the ratios of the placebo adjusted change in means. Analysis results will be presented for the change in means.

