14.3.6.1	Continuous Glucose Monitoring – Number of Subjects Outside Observed Value Reference Ranges by Day (Safety Population)
14.3.6.2	Continuous Glucose Monitoring – Number of Subjects Outside Observed Value Reference Ranges by Number of Days (Safety Population)

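### SAP 2.7.7 describes the CGM safety count for run-in and end of treatment only, leaving three or four of the five randomised dosing days outside it

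*SAP*

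**What the plan says.** **The rule.** SAP 2.7.7 sets out a safety summary of the CGM trace: "The number of subjects who had at least one value < 60" (no unit given), together with six high cut-offs from 125 to 250. These counts "will be summarized for the run-in and end of treatment periods for the following time intervals", namely 24-hour, daytime and nighttime.

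**The window.** SAP 2.7.7 does not define the end of treatment period. Two readings are available.
- SAP 1.3.1 states the objective as "to compare pre-treatment (Day 3) to end of treatment (Day 8) 24-hour CGM glucose", and the efficacy table titles in SAP 4.1 also attach Day 8 to end of treatment.
- SAP 2.8.1, written for the efficacy means, takes as on-treatment days "The last 2 days with at least 80% of expected measurements prior to 8 hours after the last dose". For a subject who completes dosing these are normally Days 7 and 8.

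**What is recorded.** Randomised treatment is given on Days 4 to 8 (SAP 1.2). The monitor is fitted on Day 1 and records until the morning of Day 10 (Protocol 6.4.1 and Table 1). The Protocol synopsis says "CGM Monitoring will be used throughout the entire treatment period to compare pre-treatment, treatment, and post-treatment glucose levels".

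**Related outputs.** SAP 4.1 lists Table 14.3.6.1 (subjects outside the reference ranges, by Day) and Table 14.3.6.2 (by Number of Days), both in the Safety Population. SAP 3.1 lists out-of-range CGM values (Listing 16.2.9.4). SAP 2.7.2 and Table 14.3.4 summarise hypoglycaemic events by treatment received, with no stated window.

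**The concern.** Whether a subject ever had a low reading depends on every day observed. A last-days window with a completeness rule suits a mean glucose endpoint; for an at-least-one-value count it discards information. Under SAP 2.7.7 as written, a subject with a value below 60 on Day 4 or 5 and none later is tabulated as having no low during treatment.

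Safety versus placebo is a primary objective, and comparing hypoglycaemia is a secondary one. Protocol 7.5.1 names hypoglycaemia first among the potential adverse events. The omitted days include the first exposure in each period. The Protocol schedules serum chemistry on Days 3 and 8 only within a period, so on Days 4-7 CGM is the only scheduled glucose measurement.

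The text also fits its own tables poorly. A tabulation by number of days has little to show when the treatment window holds one or two days.

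**Working it through.** The plan gives no figure to reproduce: there is no power calculation and no assumed rate of low readings. The check is therefore a count of days, followed by an illustration under declared assumptions.

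**1. Days covered (from the documents).** Analysis days run 6AM to 6AM. The last dose is at about 10PM on Day 8, and 8 hours later is 6AM on Day 9. Days 4-8 are thus 5 days, with 3 administrations a day (active or placebo): 15 in all.

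| Reading of end of treatment | Days in count | Administrations | Share of dosing days | Omitted |
|---|---|---|---|---|
| Day 8 | 1 | 3 of 15 | 1/5 = 20% | Days 4-7, 80% |
| Last two qualifying days | 2 | 6 of 15 | 2/5 = 40% | Days 4-6, 60% |
| All randomised days | 5 | 15 of 15 | 100% | none |

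**2. Share of affected subjects found (assumed rates).** Let p be the probability that a subject has any value below 60 on a given day. The documents give neither p nor the correlation between days, so p = 0.02, 0.05 and 0.10 are used, with correlation ρ from 0 to 0.3.

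For independent days, P(k) = 1 − (1 − p)^k is the probability of at least one low day in k days. At p = 0.05:
- P(1) = 0.050
- P(2) = 1 − 0.95² = 0.0975
- P(5) = 1 − 0.95⁵ = 0.226
- Share found on Day 8: 0.050/0.226 = 22%. Share found on two days: 0.0975/0.226 = 43%.

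For correlated days a beta-binomial is used, with a = p(1 − ρ)/ρ, b = (1 − p)(1 − ρ)/ρ and P(k) = 1 − ∏(b + i)/(a + b + i) for i = 0 to k − 1.

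| p | ρ | P(1)/P(5) | P(2)/P(5) |
|---|---|---|---|
| 0.02 | 0 | 0.21 | 0.41 |
| 0.05 | 0 | 0.22 | 0.43 |
| 0.10 | 0 | 0.24 | 0.46 |
| 0.02 | 0.3 | 0.34 | 0.57 |
| 0.05 | 0.3 | 0.35 | 0.58 |
| 0.10 | 0.3 | 0.37 | 0.60 |

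Results for ρ = 0.1 lie between these. The range is 21-37% for Day 8 and 41-60% for two days.

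**3. In subjects.** Each of 30 subjects receives two of the three active regimens; if balanced, 30 × 2/3 = 20 per regimen. At p = 0.05 with independent days, the expected number with a low on Days 4-8 is 20 × 0.226 = 4.5. The described count would show 20 × 0.050 = 1.0 (Day 8) or 20 × 0.0975 = 2.0 (two days).

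**4. Effect on the placebo comparison.** Take 10% per day on active and 5% on placebo, independent days (assumed for illustration).

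| Window | Active | Placebo | Difference | Ratio |
|---|---|---|---|---|
| Day 8 | 10.0% | 5.0% | 5.0 points | 2.00 |
| Two days | 19.0% | 9.75% | 9.25 points | 1.95 |
| Five days | 41.0% | 22.6% | 18.3 points | 1.81 |

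The absolute difference is smaller in the short windows; the ratio is not pulled towards 1.

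**5. Subjects who stop early.** If the last dose is the 10PM dose on Day d, there are d − 3 randomised days. The SAP 2.8.1 window follows the last dose, so it can still hold min(2, d − 3) days: up to 1 for a last dose on Day 4, and up to 2 for Days 5, 6 or 7, subject to the 80% rule. A Day 8 window holds none of them.

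**The case against.** The strongest reply is that SAP 2.7.7 is a descriptive supplement and the rest of the plan may already show what it leaves out. Table 14.3.6.1 is by day and Table 14.3.6.2 by number of days, both in the Safety Population. Listing 16.2.9.4 gives out-of-range values, and SAP 3.2 puts all subjects and all data in the listings. Figures 14.2.1.3 and 14.2.1.4 plot individual CGM values. The hypoglycaemia objective has its own analysis in SAP 2.7.2, without a window, and adverse events are recorded on every study day.

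Much of this stands. A reader might infer that lows on the earlier days appear nowhere in the report; the documents do not support that. The table shells are in a separate file, so the days those tables cover cannot be confirmed either way. What remains is that SAP 2.7.7 is the only method text for the two tables and names two periods. The listing and figures give no count by regimen. The classes behind SAP 2.7.2 rest on blood glucose (Protocol 7.3.1), and nothing says that every low CGM value becomes an event.

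A reader might also infer that early stoppers drop out of the count, a worry because "Episodes of hypoglycemia as defined in Section 7.3.1" is a listed reason for stopping study drug. That is not established. Under SAP 2.8.1 the window is anchored on the last dose and takes in the qualifying days nearest the stop. These subjects are lost only if end of treatment means Day 8, or if no day meets the 80% rule.

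**Conclusion.** The point holds for the count that SAP 2.7.7 describes. On either available reading it leaves out Days 4-7 or Days 4-6, which is 80% or 60% of the randomised dosing days, although CGM records them. That figure comes from the documents alone. The period is undefined where it is used, and the text needs reconciling with Tables 14.3.6.1 and 14.3.6.2.

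The consequence is fewer subjects counted with a low and smaller absolute differences from placebo. The 21-37% and 41-60% shares rest on assumed daily probabilities of 2-10% and between-day correlation of 0 to 0.3, and should be read as illustration.

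It is tempting to conclude that the rule biases the regimens towards no difference from placebo. The documents do not support that as a general statement: the same window applies to the placebo period, and in the illustration the ratio does not move towards 1. It could be distorted if the timing of lows or early stopping differed by regimen, but nothing in the documents establishes this.

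This is worth correcting before the tables are produced; it is not a flaw in the trial's design or data collection.

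**What to change.** Amend SAP 2.7.7 along these lines:

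> The counts will be given for (i) the run-in days and (ii) all randomised treatment in the period, from the first randomised dose on Day 4 to 8 hours after the last randomised dose, by treatment received. Every Safety Population subject with any CGM reading in the window is included, partial periods as well, and the 80% completeness rule does not apply. Day 9 is shown separately. Tables 14.3.6.1 and 14.3.6.2 cover all of these days.

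Because the last randomised dose ends the window, subjects who stop early are handled without a separate rule. Showing subject-days observed beside each count is optional; it would help the reader because the windows differ in length.

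The cost is SAP wording and slightly larger tables. The data are already collected and no study procedure changes. Reported counts of both low and high values will be higher than under the present text.
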